6.6 Storage and analysis of samples

All samples (with the exception of centrally analysed resistance samples) will be analysed at each site's local laboratory. After analysis the samples will be destroyed in accordance with local laboratory requirements. Throughout the study a total of 234ml of blood will be collected from each patient, this equates to 26ml per visit.

Collection, processing and storage instructions will be detailed in a separate laboratory manual.

6.6.1 Resistance testing

Next generation sequencing (deep sequencing) may be performed centrally to evaluate the significance of the HIV-1 mutations detected by this method, which are identified during standard population sequencing of the HIV viral load response.

Blood samples for these tests will be taken at the baseline visit and treatment phase visits (Week 4, 8, 12, 24, 36 and 48). A sample will be taken at the ETV for patients with virological failure identified outside of a scheduled visit.

Samples will be shipped on a periodic basis from the sites to ACM Global for central storage and shipped to Monogram Biosciences for analysis.

At the end of the study, samples taken from patients that do not have virological failure will be destroyed, either locally, or at ACM Global.

Collection, processing and storage instructions will be detailed in a separate laboratory manual.

See Appendix 1 for details of assessments required.

6.7 Virological Failure

Virological failure is defined as:

Insufficient virological response, either:

- HIV-1 RNA reduction < 1 log 10 copies/mL at week 12, or
- Viral load > 50 HIV-1 RNA copies/mL at week 48

Or viral rebound, which is subsequently confirmed at the following scheduled or unscheduled visit, defined as either:

- Rebound of HIV-1 RNA to >200 copies/mL after having achieved HIV-1 RNA <50 copies/mL
- Rebound of HIV RNA by >1 log 10 copies/mL from nadir value, for patients whose viral load has never been suppressed below 50 copies/mL

Local resistance testing should also be carried out in the event of viral failure from the first sample and patients should discontinue study medication and receive rescue medication at investigators discretion.

6.8 End of trial

The end of the trial is defined as the date of the last visit of the last subject undergoing the trial in any country.

The sponsor must notify the Competent Authority (CA) and main IRB/IEC of the end of a clinical trial within 90 days of its completion.

7 TRIAL MEDICATION

Name and description of investigational medicinal product(s)

At baseline, participants will be enrolled into one of two treatment arms, either a BIC-based regimen or a DRV-based regimen:

INI containing regimen (BIC-based regimen): One combined B 50mg/F 200mg/TAF 25mg tablet taken orally once daily for up to 48 weeks without regard to food.

Boosted PI regimen (DRV-based regimen): One combined D 800mg/C 150mg/F 200mg/TAF 10mg tablet taken orally once daily for up to 48 weeks with the addition of food.

Participants will take the study medication from baseline, as randomised, to week 48.

Please refer to the study specific pharmacy manual for more information.

7.1 Summary of Product Characteristics (SmPC), and Reference Safety Information (RSI)

Information about Emtricitabine (Emtriva®, F/FTC)

Emtricitabine (5-fluoro-1-[(2R, 5S)-2-(hydroxymethyl)-[1, 3]-oxathiolan-5-yl] cytosine, FTC) is a NRTI that has demonstrated potent and selective inhibition of the HIV. In HIV-infected adults, FTC is administered as a 200mg QD dose concurrently with other ARV drugs. The 200mg FTC capsule formulation was approved by the United States (US) FDA for marketing on 2 July 2003 and is available under the name Emtriva®. In the European Union (EU), marketing authorisation was granted for both the 200mg Emtriva® capsule formulation and a 10mg/mL Emtriva® oral solution formulation on 24 October 2003, with indications for the treatment of HIV infection concurrently with other ARV drugs in both adult and pediatric patients.

Further information is available in the current Prescribing Information for Emtriva®.

Information about Tenofovir alafenamide (TAF, GS-7340)

Tenofovir alafenamide (GS-7340, TAF) is a second-generation oral prodrug of tenofovir (TFV), a nucleotide analog that inhibits HIV-1 reverse transcription. TFV is metabolised intracellularly to the active metabolite, tenofovir diphosphate, a competitive inhibitor of HIV-1 RT that terminates the elongation of the viral DNA chain. The intracellular metabolism of TAF and TFV are consistent with the 600-fold enhancement in anti-HIV activity in cell culture of TAF over TFV.

Further information about the co-formulated version of TAF/FTC is available in the current Prescribing Information for Descovy®.

Information about Darunavir (Prezista®, D/DRV)

Prezista® is a PI which demonstrated potent inhibition of the HIV. DRV received marketing authorisation valid throughout the EU 12/02/2007. Co-administered with low dose ritonavir is indicated in combination with other ARV medicinal products for the treatment of HIV-1 infection in adult and paediatric patients from the age of 3 years and at least 15 kg body weight. Co-administered with cobicistat (C) is indicated in combination with other ARV medicinal products for the treatment of HIV-1 infection in adult patients. In ART-naïve adult patients the recommended dose regimen is 800 mg once daily with C 150 mg once daily or ritonavir 100 mg once daily taken with food.

Further information about DRV is available in the current Prescribing Information for Prezista®.

Information about Darunavir/Cobicistat/Emtricitabine/Tenofovir alafenamide (D/C/F/TAF) fixed dose combination (Symtuza®)

Syntuz® is a boosted PI indicated for the treatment of HIV-1 infection in adults and adolescents (aged 12 years and older with body weight at least 40 kg). Syntuz® received marketing authorisation valid throughout the EU in September 2017. The recommended dose regimen in adults and adolescents aged 12 years and older, weighing at least 40 kg, is one tablet taken once daily with food. Each film coated tablet contains 800 mg of D (as ethanolate), 150 mg of C, 200 mg of F, and 10 mg of TAF.

Further information about the D/C/F/TAF FDC is available in the current Prescribing Information for Syntuz®.

The Reference Safety Information for this regimen will be the formally approved and implemented version of the Summary of Product Characteristics for Syntuz® provided to investigators by the sponsor.

Bictegravir (BIC)

BIC is an inhibitor of HIV-1 integrase that is being evaluated for the treatment of HIV-1 infection. Antiviral testing has shown that BIC is active against a broad panel of HIV-1 viral lab strains and clinical isolates. BIC is fully active against a panel of mutant viruses with resistance to NRTIs, NNRTIs, and PIs. Integrase mutant viruses that are resistant to the INSTIs raltegravir (RAL) and elvitegravir (EVG) remain largely sensitive to BIC. Gilead Sciences (Gilead) has co-formulated BIC with the NRTI F and TAF into an FDC tablet that is suitable for once-daily use.

Further information about the B/F/TAF fix-dose tablet is available in the current Prescribing Information for Biktarvy®.

The Reference Safety Information for this regimen will be the formally approved and implemented version of the Summary of Product Characteristics for Biktarvy provided to investigators by the sponsor.

7.2 Drug storage and supply

Investigators are to ensure that the investigational medicinal product (IMP) is only used in accordance with the protocol. Drug supplies will be kept in a secure, limited access storage area under the recommended storage conditions, and accessible only to those authorised by the investigator to dispense to eligible subjects.

The investigator will ensure that records are maintained showing the receipt and dispensation for all study supplies. A drug accountability log will be kept with the investigational supplies for reconciliation purposes. This should be used to record the identification of the subject to whom the IMP was dispensed, the date and quantity dispensed, and the quantity unused/returned by the subject. This will be verified by the study monitor.

Partially used or empty containers may be destroyed by the pharmacy/designee at local site only after the study monitor has completed drug accountability. The pharmacy/designee are required to document destruction for verification by the sponsor.

Further information can be found in the pharmacy manual.

7.3 Preparation and labelling of Investigational Medicinal Product

Both the INI containing regimen (B/F/TAF) and the boosted PI regimen (D/C/F/TAF) tablets will be labelled with Annex 13 compliant labels and QP certified by PCI Pharma Services; who will supply directly to each site on request of the sponsor.

Further information can be found in the pharmacy manual.

7.4 Dosage schedules

Patients will be randomised into one of two treatment arms.

INI containing regimen (BIC-based regimen): One combined B 50mg/F 200mg/TAF 25mg tablet taken orally once daily for up to 48 weeks without regard to food.

Boosted PI regimen (DRV-based regimen): One combined D 800mg/C 150mg/F 200mg/TAF 10mg tablet to be taken orally once daily for up to 48 weeks with the addition of food.

7.5 Dosage modifications

Please refer to section 6.5 for withdrawal and stopping rules.

Treatment modification will be captured as a secondary endpoint only and modifications will be based on the treating physician's judgement.

7.6 Known drug reactions and interaction with other therapies

See section 8.2 and RSI.

Drugs that affect the study medication and that are affected by the use of the study medication accordingly must be reviewed by the Investigator and/or avoided.

7.7 Concomitant medication

For a full list of contraindicated medications, please refer to the current Prescribing Information for both Biktarvy® and Syntuza®

Prophylaxis for specific OI or TB shall be performed as per standard of care. Reference can be made to the EACS guidelines.

7.8 Trial restrictions

Please refer to inclusion and exclusion criteria listed in sections 5.1 and 5.2.

7.9 Assessment of adherence

Adherence during the trial will be monitored by subject questioning regarding missed tablets at each visit. The outcome of this questioning should be documented in the patient notes. Issues of adherence should be reported to the study monitor.

All subjects should return unused medication and containers at weeks 12, 24, 36 and 48 for pharmacy accountability purposes (see section 7.2).

7.10 Provision of treatment after the end of the trial

No post trial medication will be provided to patients. Following their last treatment visit at Week 48 patients will receive treatment as per local standard of care.

8 PHARMACOVIGILANCE

8.1 Definitions

Term	Definition
Adverse Event (AE)	Any untoward medical occurrence in a participant to whom a medicinal product has been administered, including occurrences which are not necessarily caused by or related to that product.
Adverse Reaction (AR)	An untoward and unintended response in a participant to an investigational medicinal product which is related to any dose administered to that participant. The phrase "response to an investigational medicinal product" means that a causal relationship between a trial medication and an AE is at least a reasonable possibility, i.e. the relationship cannot be ruled out. All cases judged by either the reporting medically qualified professional or the Sponsor as having a reasonable suspected causal relationship to the trial medication qualify as ARs.
Serious Adverse Event (SAE)	An SAE is any untoward medical occurrence that: 
 • results in death • is life-threatening • requires inpatient hospitalisation or prolongation of existing hospitalisation • results in persistent or significant disability/incapacity • consists of a congenital anomaly or birth defect Other 'important medical events' may also be considered serious if they jeopardise the participant or require an intervention to prevent one of the above consequences. NOTE: The term "life-threatening" in the definition of "serious" refers to an event in which the participant was at risk of death at the time of the event; it does not refer to an event which hypothetically might have caused death if it were more severe.
Serious Adverse Reaction (SAR)	An AE that is both serious and, in the opinion of the reporting Investigator, believed with reasonable probability to be due to one of the trial treatments, based on the information provided.
Suspected Unexpected Serious Adverse Reaction (SUSAR)	
 • A SAR, the nature and severity of which is not consistent with the information about the medicinal product set out in section 4.8 "Undesirable Effect" of the SmPC

"Severe" is often used to describe intensity of a specific event, which may be of relatively minor medical significance. "Seriousness" is the regulatory definition supplied above.

8.2 Operational definitions for (S)AEs

AEs observed by the Investigator, or reported by the subject, and any remedial action taken, will be recorded in the subject's CRF and should be verifiable in the subject's notes throughout the study. The nature of each event, time of onset after drug administration, duration and severity will be documented together with the Investigator's opinion of the causal relationship to the investigational product (unrelated, unlikely, possible, probable, and definite).

All subjects experiencing AEs, whether considered associated with the use of the study medication or not, must be monitored until the symptoms subside and any clinically relevant changes in laboratory values have returned to baseline, or until there is a satisfactory explanation for the changes observed.

Procedures such as surgery should not be reported as AEs. However, the medical condition for which the procedure was performed should be reported if it meets the definition of an AE. For example, an acute appendicitis that begins during the AE reporting period should be reported as the AE and the resulting appendectomy noted on the CRF.

Planned procedures such as surgery scheduled prior to the subject's enrolment into the study do not need to be reported as AEs if these are documented as planned at the screening visit.

Clinically significant changes in physical examination and blood safety profiles should also be recorded as AEs.

8.2.1 Assessment of intensity

Severity should be recorded and graded according to the ACTG Grading Scale (Appendix 2).

Note: There is a distinction between the seriousness and the intensity of an AE. Severe is a measure of intensity; thus, a severe reaction is not necessarily an SAE. For example, a headache may be severe in intensity but would not be classified as serious unless it meets one of the seriousness criteria for serious events.

All events deemed to be Grade 4 (potentially life threatening) according to the ACTG grading scale should be routinely reported as an SAE. However, there may be occasions where in the investigator's clinical judgement they do not consider the event to be life threatening therefore they do not consider the event to meet the definition of an SAE. In these cases, the investigator must document clearly in the participants source documentation that the Grade 4 event has been assessed and why in their clinical judgement they do not consider the event to be life threatening.

8.2.2 Assessment of causality

The relationship to study drug of each AE will be assessed by the PI (or a delegated clinician) using the following definitions:

DEFINITE: distinct temporal relationship with drug treatment. Known reaction to agent or chemical group or predicted by known pharmacology. Event cannot be explained by subject's clinical state or other factors.

PROBABLE: reasonable temporal relationship with drug treatment. Likely to be known reaction to agent or chemical group or predicted by known pharmacology. Event cannot easily be explained by subject's clinical state or other factors.

POSSIBLE: reasonable temporal relationship with drug treatment. Event could be explained by subject's clinical state or other factors.

UNLIKELY: poor temporal relationship with drug treatment. Event easily explained by subject's clinical state or other factors.

UNRELATED: the event occurs prior to dosing. Event or intercurrent illness is due wholly to factors other than drug treatment.

8.2.3 Collection and Follow up of Adverse Events

All AEs, however minor, will be documented in the CRF whether or not the Investigator considers the event to be treatment related.

The AE reporting period will be from consent until the subject's final study visit. In addition, any untoward event that may occur subsequent to the reporting period that the Investigator assesses as possibly, probably or definitely related to the study drug medication should also be reported as an AE.

AEs may be directly observed, reported spontaneously by the subject or by questioning the subject at each study visit.

All AEs should be followed up until they are resolved or the subject's participation in the study ends (i.e. until the final CRF is completed for that subject). In addition, all serious and non-serious AEs assessed by the Investigator as possibly related to the investigational medication should continue to be followed up to last subject visit. Such events should be followed until resolution, until no further change can reasonably be expected, or until 30 days following last subject visit.

8.2.4 Recording and Reporting of SAEs and SUSARs

Definition of an SAE can be found in section 8.1.

The SAE should be reported to the sponsor using the study specific Safety Event Reporting Form (SERF), within 24 hours of a member of the study team becoming aware of the event via e-mail to [contact] or via the fax number provided on the SERF.

All SAEs occurring from the time of written informed consent until 30 days post cessation of trial treatment must be recorded on the study specific SAE Form and sent to the sponsor within 24 hours of the research staff becoming aware of the event.

For each SAE the following information will be collected in the SERF:

- full details in medical terms and case description
- event duration (start and end dates, if applicable)
- action taken
- outcome
- seriousness criteria
- causality (i.e. relatedness to trial drug / investigation), in the opinion of the Investigator
- details of the reporter(s)

Any change of condition or other follow-up information should be sent to the sponsor in a follow up SERF as soon as it is available or at least within 24 hours of the information becoming available. Events will be followed up until the event has resolved or a final outcome has been reached.

The Sponsor representative (CI) will assess whether events suspected to be related to IMP-treatment would be considered expected or unexpected (using the formally approved and implemented version of the reference safety information (RSI) for either Syntuza® or Biktarvy®).

All SAEs assigned by the PI or delegate (or following central review) as both suspected to be related to IMP-treatment and assessed by the CI as unexpected will be classified as SUSARs. The sponsor will inform the CA, the IRB/IEC and the funder as appropriate of SUSARs within the required expedited reporting timescales. The sponsor will update the Eudravigilance database, as required.

8.3 Responsibilities

8.3.1 Principal Investigator (PI):

Checking for AEs and ARs when participants attend for treatment / follow-up.

1. Using medical judgement in assigning seriousness, and assessing causality (using the formally approved and implemented version of the reference safety information (RSI) for either Syntuza® or Biktarvy® provided to investigators by the sponsor).

2. Ensuring that all SAEs and SARs (including SUSARs) are recorded and reported to the Sponsor within 24 hours of becoming aware of the event and provide further follow-up information as soon as available.
3. Ensuring that SAEs and SARs (including SUSARs) are followed up with the Sponsor if a record of receipt is not received within 2 working days of initial reporting.
4. Ensuring that AEs and ARs are recorded and reported to the Sponsor in line with the requirements of the protocol.

8.3.2 Chief Investigator (CI) / delegate or independent clinical reviewer:

1. Clinical oversight of the safety of patients participating in the trial, including an ongoing review of the risk / benefit.
2. Using medical judgement in reviewing seriousness and causality of SAEs reported, when required.
3. Using medical judgement in assignment of expectedness for all SARs reported (using the formally approved and implemented version of the reference safety information (RSI) for either Symtuza® or Biktarvy®)
4. Review of specific SAEs and SARs in accordance with the trial risk assessment, protocol and as detailed in the Trial Risk Based Monitoring Plan, and pharmacovigilance management plan (PVMP).
5. Ensure immediate review of all SUSARs.
6. Assigning Medical Dictionary for Regulatory Activities (MedDRA) or Body System coding to all SAEs and SARs as needed.
7. Preparing the clinical sections and final sign off of the Development Safety Update Report (DSUR).

8.3.3 Sponsor:

1. Central data collection and verification of AEs, ARs, SAEs, SARs and SUSARs according to the trial protocol.
2. Reporting safety information to the CI, delegate or independent clinical reviewer for the ongoing assessment of the risk / benefit according to the Trial Risk Based Monitoring Plan, and pharmacovigilance management plan (PVMP).
3. Reporting safety information to the independent oversight committees identified for the trial (Data Safety Monitoring Board (DSMB)/Trial Steering Committee (TSC)) according to the Trial Risk Based Monitoring Plan and committee charter documents.
4. Expedited reporting of SUSARs to the CA and IRB/IEC within required timelines.
5. Notifying Investigators of SUSARs that occur within the trial.
6. Checking for (at least annually) and notifying PIs of updates to the RSI for the trial.
7. Preparing standard tables and other relevant information for the DSUR in collaboration with the CI and ensuring timely submission to the CA and IRB/IEC.

8.3.4 Data Safety Monitoring Board (DSMB):

In accordance with the DSMB Charter, periodically reviewing overall unblinded safety data to determine patterns and trends of events, or to identify safety issues, which would not be apparent on an individual case basis.

8.3.5 Trial Steering Committee (TSC):

In accordance with the Trial Terms of Reference for the TSC, periodically reviewing safety data and liaising with the DSMB regarding safety issues.

8.3.6 Endpoint Review Committee

The endpoint review committee will convene to review unblinded endpoint data, as and when required by the DSMB or TSC.

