2.4 Outcome measures/endpoints

2.4.1 Primary endpoint/outcome

- Time to failure, as the first occurrence of any of the following components:

1. Virological reasons

- a) Insufficient virological response, either:
 - a. HIV-1 RNA reduction < 1 log 10 copies/mL at week 12, or
 - b. Viral load > 50 HIV-1 RNA copies/mL at week 48
- b) Viral rebound, which is subsequently confirmed at the following scheduled or unscheduled visit, defined as either:
 - a. Rebound of HIV-1 RNA to >200 copies/mL after having achieved HIV-1 RNA <50 copies/mL
 - b. Rebound of HIV RNA by >1 log 10 copies/mL from nadir value, for patients whose viral load has never been suppressed below 50 copies/mL

2. Clinical reasons*

- a) Death related to HIV, AIDS, OI/severe BI or complications of therapy including IRIS
- b) Any new or recurrent AIDS defining event on, or after 28 days of therapy
- c) Any new serious non-AIDS defining event documented by the endpoint review committee (including severe BI, end stage liver disease, renal failure, cardiovascular event, and non-AIDS related malignant disease)
- d) Clinically relevant AEs of any grade or IRIS which require treatment interruption (lasting > 5 days) of INI or boosted PI therapy within the first 48 weeks after randomisation

Note: Discontinuation of BIC or boosted DRV followed by (within 5 days) continuation with another INI or PI, respectively, is not considered as a strategy failure or endpoint.

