12 ROLES AND RESPONSIBILITIES OF TRIAL OVERSIGHT COMMITTEES/ GROUPS & INDIVIDUALS

Three main trial management groups will be involved in the set up and management of the clinical trial.

Trial Steering Committee (TSC)

The TSC members should meet to periodically review the safety data and will liaise with the DSMB regarding any safety issues. The TSC must have a majority independent representation, including the Chair.

Data Safety Monitoring Board (DSMB)

The DSMB is the group that monitors the main safety and efficacy outcome measures and the overall conduct of the trial, with the aim of protecting the safety and interests of the trial participants.

The DSMB will meet periodically to review unblinded data. The frequency of these meetings will be detailed in a separate document, the DSMB Charter, but are planned to take place on a quarterly basis as a minimum.

Endpoint Committee

The DSMB or TSC may request the endpoint review committee meet to review the trial endpoints to determine trial outcomes.

Trial Management Group (TMG)

The TMG should meet regularly to ensure all practical details of the trial are progressing well and working well and everyone within the trial understands them.

The membership, frequency and the study aspects to be reviewed by the above groups, will be outlined in a separate document.

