Change No.	Description of Change	Rationale for Change
	1. Additional text to state that details of reporter included on the Safety Event Report Form 2. Addition of text to mention the pharmacovigilance management plan (PVMP) will be used by the CI and sponsor in assessment of safety reporting	to include the pharmacovigilance management plan (PVMP).
9.	Section 8.2.4 Recording and Reporting of SAEs and SUSARs Statement made that the Sponsor will update the Eudrvigilance database.	Compliance with Clinical Trial Regulation (EU) No 536/2014
10.	Section 8.3.6 and Section 12 Addition of details regarding Endpoint committee review	An endpoint committee may be requested ahead of any data analysis required by the DSMB or the TSC.
11.	8.8 Development Safety Update Reports Statement of intent for the sponsor to submit a single safety report for both IMP	Compliance with Clinical Trial Regulation (EU) No 536/2014
12.	9.5 Interim analysis and criteria for the premature termination of the trial Statement that there are no specific trial stopping criteria	Compliance with Clinical Trial Regulation (EU) No 536/2014
13.	13.3 Regulatory Compliance Change to reflect the trial will be conduct in compliance with Clinical Trial Regulation (EU) No 536/2014	Compliance with Clinical Trial Regulation (EU) No 536/2014
14.	13.6 Data protection and patient confidentiality Updated to comply with the Clinical Trial Regulation (EU) No 536/2014	Compliance with Clinical Trial Regulation (EU) No 536/2014
15.	Section 13.5: Change to the definition of serious breach and reporting timelines	The previously included strictly MHRA definition has hence been modified to include the Clinical Trial Regulation wording.
16.	Appendix 1: Study Flowchart Removal of “including urinary chemistry” after “Clinical Chemistry” in the description of this assessment	The words are superfluous as the actual tests required are described in the footnote 12 – removing them for clarity for the sites.
17.	Appendix 1: Change to the footnote 10 wording after the asterisk: regarding when assessments should be taken. Changing from “after baseline” to “at all visits required”	Changing this for clarity as it is ambiguous about whether urinalysis assessments should be done at all visits.

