2.2 ENDPOINTS

2.2.1 Primary endpoint/outcome

The primary endpoint is time to failure. Failure is defined as the first occurrence of any of the following components:

1. Virologic reasons

- a) Insufficient virologic response, either:
 - a. HIV-1 RNA reduction < 1 log 10 copies/mL at week 12, or
 - b. Viral load > 50 HIV-1 RNA copies/mL at week 48
- b) Viral rebound, which is subsequently confirmed at the following scheduled or unscheduled visit, defined as either:
 - a. Rebound of HIV-1 RNA to >200 copies/mL after having achieved HIV-1 RNA <50 copies/mL
 - b. Rebound of HIV RNA by >1 log 10 copies/mL from nadir value, for patients whose viral load has never been suppressed below 50 copies/mL

2. Clinical reasons

- a) Death related to HIV, AIDS, OI/severe BI or complications of therapy including IRIS
- b) Any new or recurrent AIDS defining event on, or after 28 days of therapy
- c) Any new serious non-AIDS defining event documented by the endpoint review committee (including severe BI, end stage liver disease, renal failure, cardiovascular event, and non-AIDS related malignant disease)
- d) Clinically relevant AEs of any grade or IRIS which require treatment interruption (lasting > 5 days) of INI or boosted PI therapy within the first 48 weeks after randomisation

Note: Discontinuation of BIC or boosted DRV followed by (within 5 days) continuation with another INI or PI, respectively, is not considered as a strategy failure or endpoint.

All clinical events will be validated as endpoints by the Clinical Endpoint Committee.

Clinical events are referenced in the appendices : Appendices 1 (AIDS-Defining Conditions), 2 (INSIGHT Serious Non-AIDS Events Criteria), 3 (INSIGHT Progression of HIV Disease Criteria) and 4 (Immune Reconstitution Inflammatory Syndrome Generic Criteria).

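### In this open-label trial no supplied passage provides for masked adjudication of clinical primary-endpoint events, and the only status given to the endpoint committee is unblinded

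*Combined protocol and SAP*

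**What the plan says.** Protocol v5.0, 6.1.5, makes the trial open-label for investigators, pharmacists, nurses and participants. Two texts then make the committee part of the primary endpoint, with different scope.

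- Protocol v5.0, 2.4.1, component 2c: "Any new serious non-AIDS defining event documented by the endpoint review committee". This covers serious non-AIDS events.
- SAP 2.2.1: "All clinical events will be validated as endpoints by the Clinical Endpoint Committee". This covers components 2a to 2d.

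Two texts describe how the committee works.

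- Protocol v5.0, 8.3.6: "The endpoint review committee will convene to review unblinded endpoint data, as and when required by the DSMB or TSC".
- Protocol v5.0, section 12: "The DSMB or TSC may request the endpoint review committee meet to review the trial endpoints to determine trial outcomes".

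Section 12 leaves the rest to a document outside the supplied set: "The membership, frequency and the study aspects to be reviewed by the above groups, will be outlined in a separate document". The amendment history (Appendix 9, item 10) gives the reason for adding the committee text: "An endpoint committee may be requested ahead of any data analysis required by the DSMB or the TSC". The DSMB has its own access, "periodically reviewing overall unblinded safety data to determine patterns and trends of events" (8.3.4), and section 12 extends its remit to the main efficacy outcomes and unblinded data.

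**The concern.** Where sites know the arm, masked central adjudication is the usual protection for endpoint components that need judgement. Here the committee decides whether some reported events count, yet the only description of what it sees says unblinded.

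The components differ in exposure. The virological ones are laboratory measurements and do not depend on the committee. Many clinical events have case definitions in Appendices 3 to 6. Judgement remains mainly in three places:

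- Component 2a, "Death related to HIV, AIDS, OI/severe BI or complications of therapy including IRIS", needs a ruling on relatedness.
- Component 2d needs a ruling that an adverse event was clinically relevant.
- Component 2b counts an AIDS event from day 28 outright, whereas IRIS counts under 2d only with an interruption of more than 5 days. Appendix 6 lists Pneumocystis pneumonia and toxoplasmosis among IRIS diagnoses without specific case definitions, and both are AIDS-defining in Appendix 3. Labelling such an event IRIS can take it out of the endpoint. The protocol background cites reports of more IRIS with integrase inhibitors (and a meta-analysis that did not find this), so the arm could colour that label.

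A lean towards the INI arm would raise the chance of a false non-inferiority claim. A lean towards the PI arm would cost power. The separate component analyses in SAP 7.1 might reveal a lean but would not correct it.

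**Working it through.** **Texts side by side.** Component 2c and SAP 2.2.1 make committee review a condition for an event to count. Section 8.3.6 ties meetings to a DSMB or TSC requirement, and section 12 to their request. Neither says that these are the only occasions. Protocol v1.5 names the committee in 2.4.1 but has no section on it. Its references to blinded review concern the DSMB, and in v5.0 these read unblinded. No supplied passage redacts case files or withholds the arm from adjudicators. The protocol says endpoint review committee and the SAP says Clinical Endpoint Committee; no passage equates them.

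**The plan's own figures** (protocol 9.1, SAP 4).

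- Margin: ln(0.63)/ln(0.75) = 1.606.
- Expected HR: ln(0.77)/ln(0.75) = 0.909.
- Events: 4 × (1.960 + 0.842)² / [ln(1.606/0.909)]² = 96.9, so 97 as stated.
- Evaluable patients: 97/0.24 = 404, or 202 per arm.

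The point changes none of these.

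**How much is clinical only.** Section 9.1 assumes 25% total failure and 20% virological failure in the PI arm, leaving 25 − 20 = 5 points that are clinical only. This share is uncertain. With 12.2% severe morbidity it implies an overlap of 12.2 + 20 − 25 = 7.2 points, or 7.2/12.2 = 59% of clinical failures, although 9.1 speaks of a few. The source of the 12.2% also does not list events like 2d.

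**Illustration at the margin.** Assumptions, not in the documents: true risks are 37% (INI) and 25% (PI); the INI arm also has 5 clinical-only points; a fraction x of these is rejected in the INI arm alone.

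- p = 0.37 − 0.05x; HR = ln(1 − p)/ln(0.75)
- SE = √(4/[202(p + 0.25)])
- P(non-inferiority) = Φ((ln 1.606 − ln HR)/SE − 1.96)
- Patients affected = 202 × 0.05x

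| x | p | Patients | HR | False non-inferiority |
|---|---|---|---|---|
| 0 | 0.370 | 0 | 1.606 | 2.5% |
| 0.1 | 0.365 | 1.0 | 1.579 | 3.1% |
| 0.2 | 0.360 | 2.0 | 1.551 | 3.9% |
| 0.3 | 0.355 | 3.0 | 1.524 | 4.7% |

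If clinical-only failures are instead 20% (5/25) of INI failures, p = 0.37(1 − 0.20x). Then x = 0.1 and 0.2 affect 1.5 and 3.0 patients and give 3.5% and 4.7%.

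**Equal rejection.** With the 20% share in each arm and the same x in both, the rates for x = 0.1, 0.2 and 0.3 are 2.57%, 2.64% and 2.72%. With 5 points in each arm, equal rejection slightly lowers the rate: at x = 0.1, HR = ln(0.635)/ln(0.755) = 1.616 and the rate is 2.3%.

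**Opposite lean.** With true risks of 23% and 25%, and PI-arm events rejected (p_PI = 0.25(1 − 0.20x)), power falls from 80% to 76%, 72% and 68%, for 202 × 0.25 × 0.20x = 1.0, 2.0 and 3.0 patients.

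**What this leaves out.** The calculation treats patients with both a clinical and a virological failure as failures whatever the committee decides. SAP 7.1 censors virological events at treatment discontinuation. A patient whose 2d event is rejected and who stays off treatment might then never count, which could enlarge the effect. In the other direction, the fraction x applies to all clinical-only failures, while judgement bears on only some.

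**The case against.** The strongest reply is that routine validation under the SAP and ad hoc unblinded review under 8.3.6 can coexist. The logged rationale speaks of review ahead of DSMB or TSC analyses. The SAP is written to protocol v2.0, while the change log introduces 8.3.6 with v4.0. Membership and scope sit in a document that was not supplied and that may provide for masking. All of this stands.

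A reader might therefore infer too much in two ways. One is that the committee meets only on request; the texts say when it will or may be convened and do not exclude other meetings. The other is that clinical endpoints are in fact adjudicated unblinded; the documents do not show this.

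It is also fair that case definitions narrow discretion, that most failures on the 9.1 inputs have a virological component, and that nothing supports any particular direction or size of lean. Masking would be weakest for 2d and for therapy-related deaths in 2a, two of the three places where judgement matters most.

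What the reply does not remove: section 12 gives the purpose of these meetings as determining trial outcomes, no other supplied passage sets out how routine adjudication is done, and the rule that decides whether a clinical event enters the primary analysis carries no masking provision.

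**Conclusion.** The point holds as a gap in protection and an unreconciled set of texts. It does not show biased or unmasked adjudication, and the sample size is unaffected. The supplied documents make committee review part of the primary endpoint in an open-label trial, give the committee no status other than unblinded, and nowhere provide for masked adjudication.

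The exposure is confined to the judgement-based clinical components. The figures in the working show sensitivity to a few one-sided decisions. They are not an estimate of bias: they rest on an assumed direction, an assumed 5 clinical-only points and a calculation that leaves out the SAP's censoring rule. It is a cheap improvement, worth making because the sensitivity concerns the primary comparison.

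**What to change.** Before sign-off, state in SAP 2.2.1 and in the committee charter that:

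- every potential clinical primary-endpoint event is adjudicated before database lock, from packages with arm and study-drug names redacted as far as possible;
- members who have already seen a case unblinded do not adjudicate it where the existing membership allows, and otherwise those cases are reported;
- site-reported events rejected by the committee are reported by arm.

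Leave unblinded tabulations to the DSMB, which already has them under section 12. Say whether the two committee names mean one body, and reconcile 2.4.1, 8.3.6, section 12 and SAP 2.2.1. If the separate committee document already provides for masking, a citation in SAP 2.2.1 is enough.

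The SAP is v0.3, and its section 5.1 allows an update before approval, so this is wording. Protocol v5.0 is described as the final EU version, so change the protocol text only if a further amendment is made for other reasons. The cost is redaction work by the coordinating office. Masking will stay incomplete for 2d and for deaths judged as complications of therapy, and the change does not touch open-label bias in what sites report or when they interrupt treatment.
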